# The Impact of Yttrium (Y90) Radiation Segmentectomy on Unresectable Hepatocellular Carcinoma

6. Liver ADC will also be measured in the peritumoral liver area.

## Brief Summary of mRECIST

### mRECIST for HCC

**CR** = Disappearance of any intratumoral arterial enhancement in all target lesions

**PR** = At least a 30% decrease in the sum of diameters of viable (enhancement in the arterial phase) target lesions, taking as reference the baseline sum of the diameters of target lesions

**SD** = Any cases that do not qualify for either partial response or progressive disease

**PD** = An increase of at least 20% in the sum of the diameters of viable (enhancing) target lesions, taking as reference the smallest sum of the diameters of viable (enhancing) target lesions recorded since treatment started

## Radiation segmentectomy protocol:

### c. *MAA mapping:*

- Patients will undergo pretreatment angiography under transfemoral or transradial access with conebeam CT to:
  - (1) determine vascular anatomy of the region ( $\leq 2$  Couinaud Segments)
  - (2) determine vascular supply of tumor
  - (3) prophylactically embolize vessels that may lead to aberrant deposition of radioembolic microspheres
  - (4) perform technetium-99 m macroaggregated albumin (99mTc-MAA) scans to determine lung shunt fraction (LSF) and splanchnic shunting.
- In all patients, the vessel feeding the segment(s) being targeted for treatment will be identified and catheterized using standard angiographic techniques and conebeam CT.

### d. *Dosimetry:*

- Based on the pretreatment angiography and conebeam CT, the volume of the perfused liver will be calculated on either the pretreatment CT or MRI, which will not be  $> 6$  weeks from time of MAA mapping.
- Assuming uniform distribution and complete Y decay in situ, radioactivity required for desired dose delivery to the injected tissue can be calculated using the pretreatment dose-planning formula:  
$$A = (D \times M)/50,$$
where A is the administered activity (activity of the vial that is to be infused) in gigabecquerels,  
D is the desired treatment dose in grays,

## The Impact of Yttrium (Y90) Radiation Segmentectomy on Unresectable Hepatocellular Carcinoma

and M is the mass of the tissue perfused by the microspheres in kilograms. M is determined after converting the volume of that tissue to kilograms using the conversion factor of  $1.03 \times 10^{-3} \text{ kg/cm}^{-3}$ .

- Target dose will be  $>205 \text{ Gy}$ , assuming that is the threshold for tumor destruction based on the referenced paper from Garin et al, which demonstrated response to Y90 at target doses  $> 205 \text{ Gy}$  (29).
- After treatment, actual dose delivered to the tissue is determined after correcting for fraction of activity remaining in the vial (R) and LSF, using the formula for the posttreatment dose delivered:  $D = 50 (A) (1 - LSF) (1 - R)/M$ .

### c. Delivery of Y90:

- Radiation segmentectomy will be performed with Yttrium-90, whereby a high radiation dose is delivered to the tumor via radioactive microspheres infused through the hepatic artery. The radioactive microsphere delivery device used will be glass-based (TheraSphere; BTG, Ottawa, Ontario, Canada), in which Y is an integral constituent of the biocompatible glass matrix.
- Patients will be subsequently imaged the same day with PET-CT to quantify dose to target tissue, as well as dose to the non-target liver. This will be performed on a PET-CT system (Siemens).

Patients who consent to the procedure, but cannot proceed with treatment due to dose resulting in  $>30 \text{ Gy}$  to the lungs or inability to target feeding vessels  $\leq 2$  Couinaud segments will be regarded as treatment failures.

Termination of Participation in Study to include those subjects who did not pass Y90 mapping test, as well as those who have clinical deterioration of concurrent medical conditions and those who decide to terminate participation.

Patients will undergo routine clinical surveillance at 6 weeks post-Y90, 12 weeks post-Y90, and at 3 month intervals post-Y90 for 2 years post Y-90 during which time they will be evaluated by the physician assistant/nurse practitioner and attending physicians, with assessment of their clinical performance, active medical issues, and any toxicities, as graded by the NCI CTCAE version 4.03. Follow-up will be within 7 days of scheduled times post-treatment.

	Screening	Mapping	Y90 Treatment	6 wks post	12 wks post	6 mo post	9 mo	12 mo	15 mo	18 mo	24 mo	End of Study
Informed Consent	X											
Demographics	X											
Medical History	X											
Physical Exam	X											
ECOG	X	X	X	X	X	X	X	X	X	X	X	X
Child Pugh	X											
AFP	X	X		X	X	X	X	X	X	X	X	
Prior Treatment Hx	X											
Hematology	X	X		X	X	X	X	X	X	X	X	

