## The Impact of Yttrium (Y90) Radiation Segmentectomy on Unresectable Hepatocellular Carcinoma

possibly associated with the use of TheraSphere, as described in the package labeling documents in Appendix 1, included death, hepatorenal failure, liver abscess, hepatic encephalopathy, hepatic decompensation, radiation hepatitis, radiation pneumonitis, duodenal ulcer, gastrointestinal bleeding and cholecystitis. These more severe events are now uncommon as patients with the high risk factors associated with the occurrence of these events are typically excluded from treatment with TheraSphere. Patients in whom TheraSphere should be used with caution include those with infiltrative tumor type, bulk disease (tumor volume >70% or nodules too numerous to count), AST or ALT > five times the upper limit of normal, bilirubin > 2 mg/dL, tumor volume >50% in the presence of an albumin < 3 g/dL, and those in whom extra-hepatic shunting to the lungs or gastrointestinal tract cannot be managed through standard angiographic techniques.

More recently, the technique of radiation segmentectomy utilizing TheraSphere has been described by Riaz et al. with treatment along an arterial anatomic plane confined to  $\leq 2$  Couinaud segments (>190Gy), resulting in complete pathological necrosis of targeted segments while limiting radiation exposure of non-targeted tissue.

In a prospective study, eighty-four patients with hepatocellular carcinoma confirmed by biopsy or radiographic evidence as defined by the European Association for the Study of the Liver (EASL) and American Association for the Study of Liver Disease (AASLD) criteria were treated with TheraSphere utilizing a segmental approach (Riaz A, et al). The objective of the study was to define radiation segmentectomy by calculating the dose delivered to the segment in addition to assessing safety and efficacy.

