## **RECORDING ADVERSE EVENTS**

In this study, patients should be encouraged to report adverse events spontaneously or in response to general, non-directed questions. At any time during the study, the patient may volunteer information that resembles an adverse event. Once it is determined that an adverse event has occurred, the Investigator should obtain all the information required to complete the adverse event form. Any medical management of an event and the date of resolution of the event must be recorded in the source document and on the appropriate case reports form(s).

For each AE, the following information will be recorded:

- Adverse event
- Serious/non-Serious
- Severity (Toxicity Grade)
- Action taken
- Relationship to study treatment
- Expected/Unexpected
- Date and time of onset
- Date and time of resolution

An expected adverse event is any AE, the nature or severity of which is identified in the relevant Package Insert. Any AE experienced by a subject will be followed until the AE has resolved to the investigator's or physician sub-investigator's satisfaction. If a problem still exists, then the investigator or physician sub-investigator at his/her discretion will ask the subject to come back to the clinic for further evaluation. Any serious adverse events should be managed as discussed.

Once the subject has been discharged from the study, the investigator has no obligation to seek further follow-up with the subject in order to identify new AEs. AEs ongoing at study exit will be followed to resolution. However, if the investigator becomes aware of an SAE that has occurred following the subject's discharge from the study and the

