### **PERIODIC SAFETY REPORTING**

Adverse events will be recorded on the AE form and coded using NCI CTCAE v 4.03. The investigator or physician sub-investigator will judge the severity of each AE and whether or not it is treatment-related. All AEs that occur after the initiation of trial treatment, including events likely to be related to the underlying disease or likely to represent concurrent illness, will be reported, including events present at Baseline which worsened during the trial.

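### Infused patients can be terminated for clinical deterioration, ending the active search for new adverse events and the scheduled ECOG and MRI assessments for a reason that may be related to outcome

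*Combined protocol and SAP*

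**What the plan says.** In the main body (Radiation segmentectomy protocol, c. Delivery of Y90), termination of participation covers subjects who fail the mapping test, "as well as those who have clinical deterioration of concurrent medical conditions and those who decide to terminate participation". No time limit is attached, and the plan does not say which conditions count.

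Recording Adverse Events states that after discharge "the investigator has no obligation to seek further follow-up with the subject in order to identify new AEs". It keeps two routes open. First, "AEs ongoing at study exit will be followed to resolution". Second, "if the investigator becomes aware of an SAE that has occurred following the subject's discharge from the study" and considers it at least possibly related, the event should be reported.

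Four other parts of the plan assume fuller observation:

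- Periodic Safety Reporting asks for every AE after trial treatment begins, "including events likely to be related to the underlying disease or likely to represent concurrent illness, will be reported".
- Surveillance with toxicity grading is set at 6 weeks, 12 weeks and "at 3 month intervals post-Y90 for 2 years post Y-90".
- The synopsis (Safety Analysis) applies the safety analysis to all patients at the interval visits.
- The section on Serious Adverse Device Effects discontinues the study once 5 SAEs have been recorded.

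**The concern.** The schedule shows a single Y90 treatment column. After infusion, ending participation removes observation and leaves exposure unchanged. If the reason for ending it is related to how the patient is doing, the missing data may be informative.

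That is plausible here. Eligible patients are Child-Pugh A or B7, and Child-Pugh is scheduled only at screening. Besides death, the Background lists among early serious events possibly associated with TheraSphere "hepatorenal failure, liver abscess, hepatic encephalopathy, hepatic decompensation, radiation hepatitis, radiation pneumonitis, duodenal ulcer, gastrointestinal bleeding and cholecystitis". Some of these could look, at the bedside, like worsening liver disease.

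Toxicity is a secondary endpoint in 30 patients without a control arm, so a few missed events would matter. Time to progression (TTP) is also exposed. The Progression section counts radiological progression, new extra-hepatic disease and ECOG 2 or worse, and none of these has a scheduled assessment after exit. The discontinuation rule depends on SAEs that are recorded, so it is weakened by any that are not.

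**Working it through.** The plan gives no figure on this point. Its one computed design figure, power of 0.9108, concerns the complete-response test and does not enter. The check is a comparison of sections, followed by one illustration.

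**Step 1. Does the clause reach infused patients?** Failed mapping is a separate reason in the same sentence, so deterioration is not another name for it. Nothing confines deterioration to the time before infusion. Read as written, the clause applies at any time up to 2 years.

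**Step 2. What is still captured after an infused patient exits?**

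| Event | Captured? | Source |
|---|---|---|
| The deterioration that led to exit | Yes, reportable | Periodic Safety Reporting |
| AE ongoing at exit | Yes, to resolution | Recording Adverse Events |
| New SAE, becomes known, judged at least possibly related | Yes | Recording Adverse Events |
| New SAE, not known or not judged related | Can be missed | No active search |
| New non-serious AE | Can be missed | No active search |
| Later ECOG 2 or worse, or progression on MRI | Can be missed | No scheduled assessment after exit |

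The schedule has an End of Study column with AE and ECOG assessment. The plan does not say whether a patient terminated early has that visit. Even if so, it covers the point of exit and not the remaining months.

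**Step 3. Is this reconciled elsewhere?** The synopsis wants all patients analysed at the interval visits, Periodic Safety Reporting wants all AEs including those of concurrent illness, and the schedule runs for 2 years. None of these says how a terminated patient is observed. No rule says how an early exit enters the toxicity or TTP analysis.

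**Step 4. Illustration for the 5-SAE rule.** The documents give no SAE rate, exit rate or share of missed events, so all three are assumed. Take 30 treated patients, at most one SAE each, independence, true SAE rate p, and a share m of SAEs unrecorded because of exit. The recorded count is then binomial with n = 30 and probability p(1 − m). For p = 0.20 and m = 0.20 that probability is 0.20 × 0.80 = 0.16.

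Chance of at least 5 recorded SAEs:

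| p | m = 0 | m = 0.10 | m = 0.20 | m = 0.30 | m = 0.50 |
|---|---|---|---|---|---|
| 0.10 | 0.175 | 0.128 | 0.087 | 0.055 | 0.016 |
| 0.20 | 0.745 | 0.649 | 0.537 | 0.413 | 0.175 |
| 0.30 | 0.970 | 0.937 | 0.879 | 0.785 | 0.476 |

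The expected recorded rate falls in proportion: at p = 0.20 it is 0.18, 0.16, 0.14 and 0.10 for the four values of m above zero. The table shows direction and sensitivity. It does not estimate what will happen in this trial.

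**The case against.** The strongest reply is that little is lost. The triggering deterioration is itself reportable and, if serious, counts toward the 5-event rule. If it is ongoing at exit it is followed, so its worsening should be seen. Related SAEs that come to light are still reported. Only a new event after exit can be missed. All of this stands, and it rules out the reading that toxicity follow-up simply stops. What remains is that the SAE route is passive and filtered by causality, and that no route exists for new non-serious AEs.

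A second reply concerns who is removed. A reader might infer that these are the patients most likely to have toxicity, because liver disease is their main concurrent condition. The documents do not say so. Periodic Safety Reporting names underlying disease and concurrent illness separately, which may point the other way. The termination sentence also directly follows a rule about patients who cannot proceed to treatment, so the authors may have had the pre-infusion period in mind. The link to outcome is therefore plausible but unproven. The undefined term is itself a reason to clarify the text.

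Third, a reader might cite Table 5 as evidence of late hepatic toxicity that would be lost, for example bilirubin 7/53 (13%) at 3-6 months or albumin 4/19 (21%) at 12-24 months. It does not serve. Baselines were 3/102 and 5/102, the bilirubin p value at 3-6 months is 0.27, bilirubin at 12-24 months is 0/19, and the text introducing the table says many abnormalities were present at baseline and did not change over 24 months.

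Fourth, Periodic Safety Reporting defines which events are reportable and sets no duration. The sections are unreconciled; a flat contradiction would be too strong a description.

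**Conclusion.** The concern holds in limited form. Taken together, the termination clause and the sentence on discharge allow active AE search and scheduled ECOG and MRI assessment to end early in infused patients, for a reason that may be related to outcome. This assumes that termination of participation and discharge from the study mean the same thing, which is reasonable but not stated.

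Missed new events would lower the reported toxicity rate and the count for the 5-SAE rule. Patients who exit would ordinarily be censored for TTP. If exit precedes progression, that censoring is informative and TTP would look longer than it is. It would go too far to say that such patients are removed from the TTP analysis, because the plan has no rule for them.

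The size cannot be derived from the documents. The table above rests wholly on assumed rates. The point merits an amendment because the stated rule, followed as written, can bias two secondary endpoints and the repair is cheap.

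**What to change.** 1. In the termination paragraph, limit the deterioration clause to patients not yet infused.
2. State that infused patients stay in safety and outcome follow-up to 24 months unless they die or withdraw consent. If a patient cannot attend, collect AEs, ECOG, and survival or progression status by telephone or chart review on the scheduled dates, with MRI when feasible.
3. In Recording Adverse Events, limit the sentence that removes the duty to look for new AEs to patients who completed 24 months or withdrew consent.
4. State how the remaining early exits are handled in the toxicity and TTP analyses.

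These changes concern data collection only and leave clinical care to the treating team. The cost is amendment wording and a few extra contacts. The AE rates may come out slightly less favourable.

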# The Impact of Yttrium (Y90) Radiation Segmentectomy on Unresectable Hepatocellular Carcinoma

Coagulation	X	X		X	X	X	X	X	X	X	X	
Chemistry Panel, LFTs	X	X		X	X	X	X	X	X	X	X	
Serum Pregnancy	X	X	X									
Liver Volume/Tumor Mass		X										
Review Eligibility	X											
Hepatic Angio, MAA scan, Dose Calculation		X										
Quantify dose on PET/CT			X									
MRI abd/pelvis	X			X	X	X	X	X	X	X	X	
CT of chest	X							X			X	
Assess/Report Adverse Events	X			X	X	X	X	X	X	X	X	X
Review Record Study Treatment				X	X	X	X	X	X	X	X	X
Final Efficacy documentation												X

Data from this trial will be captured on case reporting forms (CRFs). An audit trail will be maintained to document all data changes in the database.

Procedures will be followed to ensure the validity and accuracy of the clinical database. The investigator will sign and date all indicated places on the CRFs. This signature will indicate that thorough inspection of the data has been made and will certify that the Site Investigator has reviewed and approved the data contained on the forms.

## DATA MANAGEMENT

The investigator will ensure that trial data quality is maintained to current standards of Good Clinical Practice and that data are submitted in a timely manner as outlined in the protocol and supporting documentation. The investigator must sign an affirmation statement verifying the content of all subjects' CRFs. Errors must be corrected in accordance with EDC data entry guidelines.

## ADVERSE EVENTS

Adverse experience will be considered synonymous with the term adverse event and vice versa.

## DEFINITIONS OF AE/SAE FOR DRUGS

### Adverse Device Effect (ADE)

An adverse device effect is an adverse event (AE – previously defined) related to a medical device and includes any event resulting from insufficiencies or inadequacies in the instructions for use or the deployment, implantation, installation or malfunction of the

# The Impact of Yttrium (Y90) Radiation Segmentectomy on Unresectable Hepatocellular Carcinoma

device; any event that is the result of user error; or any potential adverse device effect which might have occurred if suitable action had not been taken or intervention had not been made or if circumstances had been less fortunate.

## **Serious Adverse Device Effect (SADE)**

A Serious Adverse Device Effect is an adverse device effect that has resulted in any of the consequences characteristic of a serious adverse event (SAE – previously defined) or might have led to any of these consequences if suitable action had not been taken; intervention had not been made or circumstances had been less fortunate. This is classified as Grade 3-4 as per the NCI CTCAE v4.03. If 5 Serious Adverse Events are recorded, the study will be discontinued.

## **Unanticipated Adverse Device Event (UADE)**

An unanticipated adverse device effect is any serious adverse effect which by its nature, incidence, severity and outcome has not been identified in the risk assessment, the informed consent form as well as the protocol.

## **RECORDING ADVERSE EVENTS**

In this study, patients should be encouraged to report adverse events spontaneously or in response to general, non-directed questions. At any time during the study, the patient may volunteer information that resembles an adverse event. Once it is determined that an adverse event has occurred, the Investigator should obtain all the information required to complete the adverse event form. Any medical management of an event and the date of resolution of the event must be recorded in the source document and on the appropriate case reports form(s).

For each AE, the following information will be recorded:

- Adverse event
- Serious/non-Serious
- Severity (Toxicity Grade)
- Action taken
- Relationship to study treatment
- Expected/Unexpected
- Date and time of onset
- Date and time of resolution

An expected adverse event is any AE, the nature or severity of which is identified in the relevant Package Insert. Any AE experienced by a subject will be followed until the AE has resolved to the investigator's or physician sub-investigator's satisfaction. If a problem still exists, then the investigator or physician sub-investigator at his/her discretion will ask the subject to come back to the clinic for further evaluation. Any serious adverse events should be managed as discussed.

Once the subject has been discharged from the study, the investigator has no obligation to seek further follow-up with the subject in order to identify new AEs. AEs ongoing at study exit will be followed to resolution. However, if the investigator becomes aware of an SAE that has occurred following the subject's discharge from the study and the

## The Impact of Yttrium (Y90) Radiation Segmentectomy on Unresectable Hepatocellular Carcinoma

investigator considers the SAE possibly, probably, or definitely related to a study drug or device, then the investigator should report the SAE as described in the protocol.

### **CAUSALITY (RELATIONSHIP TO MEDICAL DEVICE) ASSESSMENT**

The investigator or physician sub-investigator must indicate whether he/she believes the AE is not related, unlikely related, possibly related (reasonable possibility that the medical device caused the AE), probably related, or definitely related to the medical device. An adverse event becomes an adverse device effect when the adverse event is considered associated with the use of the test device if the attribution is Possibly, Probably or Definitely Related.

### **PERIODIC SAFETY REPORTING**

Adverse events will be recorded on the AE form and coded using NCI CTCAE v 4.03. The investigator or physician sub-investigator will judge the severity of each AE and whether or not it is treatment-related. All AEs that occur after the initiation of trial treatment, including events likely to be related to the underlying disease or likely to represent concurrent illness, will be reported, including events present at Baseline which worsened during the trial.

